**Study sites**: Three Atlanta area HIV/AIDS primary care clinics will be recruitment sites: The Ponce de Leon Center of the Grady Health System, the Emory Hospital Infectious Diseases Clinic, and AbsoluteCARE, Inc. Patients served represent a wide range of SES and demographic groups across all clinics (> 50% of patients are African American). Combined, the clinics serve a total of nearly 8900 patients of whom **about 2500 are aged 50 and over**. This provides a substantial pool of potential participants.

Assessments Time Points. At baseline (BL), all study measures listed below (see tables 4-7) will be administered. These same measures will also be completed at T1 (13-15 weeks post-baseline), T2 (28-30 weeks post-baseline), and T3 (56-58 weeks post-baseline). The total time to complete each study visit (except the

booster) is expected to be approximately 6-8 hours. The PIs' earlier studies with similar populations included study visits lasting a similar length of time. With mandatory, scheduled breaks, snacks, and lunch provided (post-blood collection), participants are able to complete each study visit over two days.

**Study arms.** Randomization procedures. Randomization will occur after completion of the first baseline assessment; after the study cardiologist reviews the participant EKGs from a treadmill stress test and prior to the second baseline assessment visit. Randomization of participants will be stratified by site to ensure a similar distribution in subjects' demographics and estimated premorbid IQ between the treatment groups. At each of the three recruiting sites, participants will be randomized to the *Let's Move* intervention arm or to the *Let's Flex* attention control arm in a 2:1 ratio. During the first and second baseline assessment visits, participant will be provided a schedule of events, copies of informed consent and project

office phone numbers, and instructions on how to prepare for the first evaluation which will include fasting blood work and the exercise treadmill test.

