## Intervention Arm: Let's Move Program.

Treadmill Test - Dose-specific exercise will be based on maximum heart rate (HR) obtained during a symptom limited, modified Balke or Bruce treadmill test conducted by an exercise physiologist and supervising clinician at the Clinical Research Network (CRN). Target heart rate (THR) using the 60% to 70% of maximum HR achieved on the cardiopulmonary exercise test will be used to monitor the intensity and training response for aerobic exercise.

▶ Home Exercise Training – After the study cardiologist clears a participant to continue in the study after reviewing their EKG from a treadmill stress test, a second participant visit within 12-weeks post treadmill test will be conducted at the research office to develop an individualized "exercise prescription" to be done at the participant's home to ensure that participants achieve adequate training stimulus. Each participant will be provided with an individualized target heart rate zone based on the treadmill testing results. Under the supervision of a research staff, participants will be instructed to begin the walking sessions at 60% of target heart rate and increase to 70% by week 5 as shown in Table 3. In our pilot work, a progressive moderate intensity level exercise program yielded positive outcomes with no adverse events, was appealing to participants and adherence rates were 80% or higher.

	Weeks 1-2	Weeks 3-4	Weeks 5-8	Weeks 9-12	Weeks 13-58
					(maintenance)
Intensity	60%	60%	70%	70%	70%
Duration	30 minutes	45 minutes	45 minutes	60 minutes	60 minutes
Frequency	5 times per week				
	week	week	week	week	

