**Process Evaluation:** Documentation of the delivery of the intervention will be provided through research assessment visits and telephone calls, plus participant evaluation of the group sessions. The Fitbits, polar HR monitor data, step logs, and pedometer data will be monitored during the group sessions and telephone calls and collected at each scheduled study visit. Research staff performing the intervention will use a quality indicator form to record their delivery of specific aspects of the intervention each session, difficulties encountered, and questions or issues raised by participants. These data will be entered into the database in the form of field notes which will be text-analyzed for themes. Participants will also be asked to evaluate the benefits of the sessions as well as make suggestions for improvement.

Attention Control (AC) Arm: *Let's Flex Program*. As delineated in the figure above, all study assessments will also be completed by the Let's Flex attention control condition participants. Content of the sessions and all contact will be on flexibility and stretching and will provide control for the possible confounding variable of receiving an exercise program and is also expected to reduce attrition and patient dissatisfaction and to better ensure concealment of group allocation. These time-equivalent flexibility/stretching movements have been previously piloted and were well received, but were not strong enough to influence cardiovascular or biomarker outcomes. For ethical and cardiovascular health reasons, the AC group will be advised to exercise, but will not be provided with education on exercise, nor receive an exercise prescription. The AC group will only be provided with stretching information. Let's Flex participants will document adherence to the flexibility protocol on a Let's Flex log that will be reviewed during groups/visits. Assessments at each time point indicated in tables 4-7 will also be completed with the AC group identical to the intervention group.

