### Study Assessments.

Cognitive Outcome Measures will be used to measure the primary outcome variables at BL, T1, T2 and T3 assessments. Cognitive outcome measures will be measured at the second visit for baseline after the study cardiologist has cleared a participant to continue with the exercise study after reviewing their EKG from a treadmill stress test. These outcome measures have been effectively used to examine neurocognitive functioning and treatment effectiveness in numerous clinical trials and in persons with wide-ranging medical conditions, including those who have HIV/AIDS. Table 4 lists the selected measures for the proposed study, domains assessed, a brief description of each, primary variable(s), and administration time. The outcome measures reflect the areas of executive functioning, episodic memory, and processing speed hypothesized to be affected by the exercise intervention based on findings in the research literature. Four parallel forms are available for the memory measures to reduce potential practice effects associated with repeated presentation of the same to-be-learned stimuli. [name], the project neuropsychologist, will provide outcome assessment training and continuous monitoring of data collection and quality. The examiner will code the reliability of each test score, any alteration of standard procedure, and the reason.

Table 4. Cognitive Outcome Measures			
Measures	Description	Time (min.)	
Stroop Color and Word Test	The Stroop Color and Word Test consists of a Word Page with color words printed in black ink, a Color Page with 'Xs' printed in color, and a color-Word Page with words from the first page printed in colors from the second page (the color and the word do not match). The respondent goes down each sheet reading words or naming the ink colors as quickly as possible within a time limit. The test yields three scores based on the number of items completed on each of the three stimulus sheets		
Trail Making Test A & B	The Trail Making Test is a neuropsychological test of visual attention and task switching. It consists of two parts in which the subject is instructed to connect a set of 25 dots as quickly as possible while still maintaining accuracy. The test can provide information about visual search speed, scanning, speed of processing, mental flexibility, as well as executive functioning. It is sensitive to detecting several cognitive impairments such as Alzheimer's disease and dementia		

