NIH Toolbox	Computerized cognitive tests developed and distributed by the NIH. Tests include Pattern Comparison Processing Speed Test, Picture Vocabulary Test, Reading Recognition Test, Dimensional Change Card Sort Test, Flanker Inhibitory Control and Attention Test, Picture Sequence Memory Test, List Sorting Working Memory Test, and Oral Symbol Digit Test	

Blood collection procedures: After overnight fasting, all blood samples will be collected with an intravenous (IV) catheter will be placed into a forearm vein or hand. Blood samples will be collected by a research staff or laboratory assistant trained in blood drawing techniques after 30 minutes of rest between 8-11:30 am (to control for circadian variation) in EDTA or Heparin tubes and immediately placed on ice. Where indicated, blood will be spun at 3,000 rpm for 15 minutes at 4C. Plasma samples will be coded, labeled and will be aliquoted into pre-cooled siliconized polypropylene tubes and stored at -80C until assayed for relevant biomarkers. Processing and analyses of specimens will be performed according to manufacturer ELISA recommendations. Blood collection for the measures in Table 5 will occur at **Baseline, T1, T2 and T3 assessments.** When the study is completed, the blood sample will be destroyed.

Flow mediated Dilation (FMD): A forearm test will be conducted to measure endothelial function at **Baseline, T1, T2, and T3 assessments** after overnight fasting. Participants will have a blood pressure cuff placed around one of their arms. The blood pressure cuff will be inflated and deflated and a trained clinical staff will use an ultrasound device to take measurements of the blood flow in the participants arm.

Table 5. Biological Measures			
Measures	Description		
Inflammatory Biomarke	rs		
Soluble Cluster of Differentiation 14 (sCD14)	Marker of monocyte activation, is associated with neurocognitive impairment and HANDs and higher mortality in PLWH. 		
Interleukin 6 (IL-6)	IL-6 is a well-established pro-inflammatory cytokine known to contribute to the pathogenesis of insulin resistance that contributes to increased risk of CVD and CI through inflammation and promotion of endothelial vascular dysfunction. IL-6 has also been associated with both depression and fatigue in both medically ill and medically healthy individuals. 		

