The potential risks to subjects are anticipated to be minimal, and the anticipated benefits to patients enrolled in the study are potentially high. The majority of those who participate in aerobic exercise are expected to show an improvement in cognitive function, physiological status, aerobic capacity and QOL. Because CI and physical inactivity contributes to physical function decline and poor clinical outcomes in persons with HIV, improvement of physical function has the potential to significantly reduce the burden associated with this disorder and has potentially cost savings benefits. Based on our previous experience, we anticipate that the Let's Flex group may have an improvement in psychological functioning and QOL as a result of the contact with the research team members, but it will likely be of shorter duration than the intervention groups, and have no benefit on any of the other outcome variables. In addition, potentially Let's Flex participants may improve in HIV self-care behaviors based on the additional knowledge and education provided in the education sessions.

The potential knowledge to be gained from this study include a better understanding of the underlying mechanisms that contribute to CI and the influence of an aerobic exercise program on cognition, aerobic capacity and novel biomarkers. Moreover, testing a home-based intervention may increase future scalability and uptake of the intervention if efficacious.

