AIM 1. Neurocognitive Improvement: We expect the primary cognitive improvements to be found in executive skill, episodic memory, and processing speed (as measured by CANTAB) since these skills are most susceptible to the effects of exercise. As recommended by Grant and Marcotte, demographically adjusted scores will be used to test for intervention effects between the treatment and attention control conditions over the study time period. To adjust for the effects of practice from repeated testing, we develop z-scores for each of the neuropsychological assessment tests using the regression-based method. Specifically, we first use multiple regression from control participants' test scores to derive the norms for change across visit times. Then we calculate the z-score by adjusting the raw test score with the expected normal follow-up score based on the subject's baseline characteristics using the multiple regression model. This method accounts not only for the effects of practice but also test-retest reliability (e.g., regression to the mean, ceiling and floor effects) and is the method suggested for use with clinical samples. The z-scores will be used as the outcome measures in the following statistical analyses. We will then use the confidence-interval-based method to classify whether a subject has shown improved cognitive functioning when comparing to the norms for change. Specifically, we will define "no change" on each cognitive test using a 90% confidence interval (CI) based on the norms generated from the control subjects' data. Then, participants who score above the upper bound of the 90% CI, i.e. in the top 5% of the normal distribution, will be defined as "improved", while those within the 90% CI defined as "no change" and those below the lower bound of the CI defined as "decliners". Modeling and Hypothesis testing. Repeated measures analysis will be performed to model the z-scores of the NP tests, the classified improvement status and other outcome measures longitudinally to test whether there are differences between the two intervention groups in terms of executive skill, episodic memory and information

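### The primary cognitive baseline is taken after randomisation, and nothing in the available text masks the examiners or withholds allocation until the battery is done

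*Combined protocol and SAP*

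**What the plan says.** - **When randomisation happens.** Section 5, Study arms (Randomization procedures) places it after the first baseline assessment, "after the study cardiologist reviews the participant EKGs from a treadmill stress test and prior to the second baseline assessment visit".
- **When the primary baseline is taken.** Section 5, Study Assessments calls the cognitive battery the measure of the primary outcome variables and states: "Cognitive outcome measures will be measured at the second visit for baseline after the study cardiologist has cleared a participant".
- **What else may happen then.** Under Let's Move, Home Exercise Training, "a second participant visit within 12-weeks post treadmill test will be conducted at the research office to develop an individualized" exercise prescription. This is probably the same visit, but no sentence says so, and the point does not depend on it.
- **Concealment and staffing.** The Attention Control paragraph says the control content is expected "to better ensure concealment of group allocation". The Risks section says the staff who teach stretching are not involved with the intervention groups.
- **Examiners.** The project neuropsychologist trains them and monitors data collection. "The examiner will code the reliability of each test score, any alteration of standard procedure, and the reason".
- **Use of baseline.** Section 7, Aim 1 forms each z-score by comparing a follow-up score with the score expected from the participant's "baseline characteristics using the multiple regression model", with norms derived from the control arm.

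**The concern.** Adjusting for baseline is safe when allocation cannot have affected baseline. Here the assignment already exists when the primary outcome is first measured, and the plan does not say who knows it.

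The study team holds a directional expectation. The anticipated-benefits text in Section 5 says "The majority of those who participate in aerobic exercise are expected to show an improvement in cognitive function" and foresees no such benefit for Let's Flex. An examiner who knows the arm could hold that expectation while administering and judging the baseline tests. A participant who knows the arm could try harder or less hard. A baseline raised in Let's Move would bias the comparison against the intervention; a lowered one would favour it.

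There is a secondary consequence. Someone randomised who never completes the second visit has no primary baseline, although Section 7 commits to intent-to-treat. The documents do not allow an estimate of how many this would be.

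**Working it through.** **Order of events, from the two controlling paragraphs**

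1. First baseline visit, including the treadmill test.
2. Cardiologist reviews the EKG.
3. Randomisation (Study arms).
4. Second baseline visit: cognitive battery (Study Assessments).

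Step 3 precedes step 4 by the plan's own rule. The MoCA memory subtest and Oral Trail Making Test B precede randomisation, but they are eligibility screens in Section 6, not the outcome battery.

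**Search for a safeguard**

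| Text | What it covers | Masks examiners or delays disclosure? |
|---|---|---|
| Attention Control paragraph | Concealment as an expected benefit of the control content; no person, method or release time | No |
| Risks, Let's Flex | Separation of stretching instructors | No |
| Study Assessments | Examiner training, monitoring, reliability coding | No |
| Quality and fidelity | Manuals and scripts for consistent delivery | Not stated |

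The figure to which the Attention Control paragraph refers is not shown in the available text and may say more.

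**How a baseline shift would carry through**

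The plan gives no figure to reproduce. The inputs below are assumptions, not values from the documents: a shift *d* in one arm's mean baseline (in SDs), a slope *b* of follow-up on baseline, equal SDs at both times, and the baseline score included in the norming regression.

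- Adjusted effect = (difference in follow-up means) − *b* × (difference in baseline means), so the raw bias has size *b* × *d*.
- The residual SD is √(1 − *b*²), so the bias on the z-score scale is *b* × *d* / √(1 − *b*²).

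For *d* = 0.10:

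- *b* = 0.5: raw 0.5 × 0.10 = 0.050; z-scale 0.050 / √0.75 = 0.058.
- *b* = 0.8: raw 0.8 × 0.10 = 0.080; z-scale 0.080 / 0.6 = 0.133.

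| Assumed shift *d* | Raw bias, *b* = 0.5 to 0.8 | z-scale bias, *b* = 0.5 to 0.8 |
|---|---|---|
| 0 | 0 | 0 |
| 0.05 | 0.025 to 0.040 | 0.029 to 0.067 |
| 0.10 | 0.050 to 0.080 | 0.058 to 0.133 |
| 0.20 | 0.100 to 0.160 | 0.115 to 0.267 |

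A simulation with control-only norms, no true effect and 6,000 runs per setting agrees. With 132 v 68 and Let's Move shifted up by 0.10, the mean raw bias was −0.051 (*b* = 0.5) and −0.080 (*b* = 0.8), and the z-scale bias −0.060 and −0.135. Shifting Let's Flex up instead reversed the signs (+0.051 and +0.081 raw; +0.059 and +0.136 on the z-scale). With 107 v 53, taking Let's Move as the larger arm in line with the 2:1 ratio, the results were −0.049 and −0.080 raw, −0.057 and −0.136 on the z-scale. The size therefore does not depend on which of the documents' sample sizes applies. The simulation confirms the formula; it is no evidence that a shift occurs.

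I have not expressed the bias as a share of the 0.37 detectable effect in Section 7, because that section does not say what 0.37 is standardised to.

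**The case against.** The strongest reply is that generating an assignment is not the same as disclosing it. No sentence says that the participant or examiner learns the arm before the battery, and the promised manuals and visit scripts, or the missing figure, might contain a masking rule. This stands as a limit: the harm is possible, not shown. It does not supply the missing safeguard, and a stated non-disclosure rule is exactly what would settle it.

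Several features reduce the risk:

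- No arm-specific training is described before the second visit, so only knowledge of allocation could act.
- Many tests are timed, and the NIH Toolbox items are "Computerized cognitive tests developed and distributed by the NIH".
- The neuropsychologist monitors data quality.
- The examiner's reliability code is a quality judgement; the plan does not say that it changes the analysed score.
- The recorded expectation concerns improvement over time and belongs to the team, so extending it to participants' baseline performance is inference.

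These make a large shift less likely. They do not rule one out, because examiners still administer many of the tests and effort can respond to known allocation.

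The plan also does not state outright that the baseline score enters the norming regression. It does claim that the method handles regression to the mean and test-retest reliability, which is hard to do without that score.

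On missing baselines, Section 7 plans REML, which retains partial cases, and a general sensitivity analysis, and the drug-screening text reschedules tests rather than dropping them. None of this replaces a baseline that was never taken.

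Finally, examiner masking at T1 to T3 is a wider question, which a change to the baseline sequence leaves open. That is correct.

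**Conclusion.** The concern holds. The plan's stated sequence puts the primary cognitive baseline after randomisation, and no available text masks the cognitive examiners or delays disclosure. Confidence is high on those two facts.

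The occurrence, direction and size of any bias are unknown. The illustrative 0.06 to 0.13 residual SD rests on an assumed 0.10 SD shift, a slope of 0.5 to 0.8, equal SDs, and inclusion of the baseline score in the norms. It scales linearly with the shift. This should be fixed because it exposes the primary outcome and the remedy is cheap.

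**What to change.** Replace the timing sentence in Section 5, Study arms (Randomization procedures) with:

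> Randomization will occur after cardiologist clearance and after the baseline cognitive battery is completed at the second baseline visit, and before any arm-specific prescription or stretching instruction.

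If that is not workable, keep the timing and add:

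> Allocation will not be disclosed to the participant or the cognitive examiner until the baseline cognitive battery is complete.

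The first option also removes the secondary problem of randomised participants with no primary baseline. The second addresses only the bias.

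**Cost.** Neither option adds an assessment. Under the first, the arm is known later. The retention section pays for the two baseline visits separately, so the two assessment days are probably those visits and no spare day is shown. Arm-specific staff would need to be available at the end of the second visit, or instruction would follow shortly after, perhaps at a further short contact. Instruction must still precede the first motivational interviewing group, because participants are to have begun their home programme by then. Those groups start after the second visit and within 4 weeks, which leaves time to form them. The fallback needs no rescheduling of randomisation.

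Both options protect the baseline cognitive battery only. Whether examiners are masked at T1, T2 and T3 should be stated separately.

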## Intervention Arm: Let's Move Program.

Treadmill Test - Dose-specific exercise will be based on maximum heart rate (HR) obtained during a symptom limited, modified Balke or Bruce treadmill test conducted by an exercise physiologist and supervising clinician at the Clinical Research Network (CRN). Target heart rate (THR) using the 60% to 70% of maximum HR achieved on the cardiopulmonary exercise test will be used to monitor the intensity and training response for aerobic exercise.

▶ Home Exercise Training – After the study cardiologist clears a participant to continue in the study after reviewing their EKG from a treadmill stress test, a second participant visit within 12-weeks post treadmill test will be conducted at the research office to develop an individualized "exercise prescription" to be done at the participant's home to ensure that participants achieve adequate training stimulus. Each participant will be provided with an individualized target heart rate zone based on the treadmill testing results. Under the supervision of a research staff, participants will be instructed to begin the walking sessions at 60% of target heart rate and increase to 70% by week 5 as shown in Table 3. In our pilot work, a progressive moderate intensity level exercise program yielded positive outcomes with no adverse events, was appealing to participants and adherence rates were 80% or higher.

	Weeks 1-2	Weeks 3-4	Weeks 5-8	Weeks 9-12	Weeks 13-58
					(maintenance)
Intensity	60%	60%	70%	70%	70%
Duration	30 minutes	45 minutes	45 minutes	60 minutes	60 minutes
Frequency	5 times per week				
	week	week	week	week	

